8.3 Multiple Comparisons and Multiplicity

The K-stage group-sequential design for efficacy introduces a multiple test problem. Therefore, the familywise error rate (FWER) will be adjusted via an error-spending function ([Jennison and Turnbull 1999](#)) for each stage of the interim analyses that maintains the alpha for each interim analysis.

The cumulative error-spending-function to be used is defined as:

$$E(t; \rho) = \begin{cases} 1, & \text{if } t \geq 1 \\ t^\rho, & \text{if } 0 < t < 1, \\ 0, & \text{otherwise} \end{cases}$$

where ρ is the power parameter (for this trial chosen as $\rho=2$) and where t is the information fraction. That is, with a specified error of α , the cumulative error spending at each stage k is $\alpha E(\Pi_k; \rho)$, with Π_k as information fraction at each stage k . For example for $k=3$ and equally spaced interim analyses this would lead to cumulative errors of $(1/3)^2$, $(2/3)^2$ and 1, multiplied by α .

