14. INTERIM ANALYSIS

14.1 Interim Analysis

As the circulation of influenza viruses is seasonal and the event rates of influenza are difficult to predict, this study is group sequentially, with a case count-driven interim analysis if decided by the Sponsor. The goal of the Interim Analyses is, first, to minimize the risk of not being able to take a significant test decision after the end of the study, and second, to be able to stop the study for early evidence of efficacy.

The number of laboratory-confirmed influenza cases will be reviewed on a regular basis. If decided by the Sponsor and after observing at least 50% of planned events meeting the co-primary endpoint, an interim analysis for efficacy may be performed for evaluation by a DMC.

- If the number of RT-PCR confirmed influenza cases is less or equal to 190 overall, no interim analysis for efficacy may be done and the study will be extended because the probability to make a conclusion for efficacy is too low.
- If the number of RT-PCR confirmed influenza cases is greater or equal to 191 but less than 381 unblinded interim analyses for efficacy may be performed for evaluation by the DMC (see below for description and DMC charter). To maintain the overall alpha, $\alpha = 2.5\%$ (1-sided), for the hypotheses testing for the primary objectives, an error-spending-function will be used. The benefit of using an error-spending-function is that no maximum number of analysis stages and the timing of the analyses need to be pre-specified, what in practice means that the duration of the study in terms of number of seasons can be left open. In this case α -boundaries, forming the adjusted probabilities for the type I error, are calculated using error-spending function and if the p-values for both primary objectives are lower than the respective α -boundary the trial stops early (i.e., without reaching the targeted number of cases of 381) for efficacy. Otherwise, the trial continues enrollment. Decisions to stop or continue the trial will be made on the basis of discussions between the DMC and Senior Management.

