At each interim stage, α -boundaries, forming the adjusted probabilities for the type 1 error, are calculated using error-spending function and if the p-value for the test of primary objective is lower than the respective α -boundary the trial stops for efficacy at this stage.

In other words the trial stops early for efficacy if data collected at this stage allows to demonstrate both primary and co-primary efficacy objectives (reject null-hypothesis). Further guided by efficacy estimates of QIVc described in secondary efficacy objective 4 (prevention of PCR confirmed influenza antigenic matched to the strains selected for the seasonal vaccine). Otherwise, the trial continues to the next stage and more subjects will be enrolled.

The cumulative O'Brien-Fleming type error-spending-function ([Lan and DeMets, 1983](#), option ERRFUNCOBF in SAS[®] PROC SEQDESIGN) will be used for both α - and β -boundaries; the error-spending function is defined as:

$$E(t; a) = \begin{cases} 1 & \text{if } t \geq 1 \\ \frac{1}{a} 2 (1 - \Phi(\frac{z(1-a/2)}{\sqrt{t}})) & \text{if } 0 < t < 1 \\ 0 & \text{otherwise} \end{cases}$$

where a equals α for α spending function and β for beta spending function, and where t is the information fraction.

If the trial proceeds to the final analysis, the boundary for rejection of null hypothesis is identical to the type 1 error (that is as the 0.025 one-sided alpha level) with power specified for the overall design, and the trial stops to either reject or not reject the null hypothesis of the primary objective.

Additional interim analyses may be requested at a future date (by the DMC), particularly if the first interim analysis is conducted soon after 191 cases of influenza have been reported. In this case, the DMC may request that a second interim analysis be conducted to allow for greater accuracy to determine if the trial should stop or continue.

Any modifications of a trial design (i.e. introducing additional interim analysis stage) and calculations of number of subjects to be additionally enrolled will be based on the assumptions as defined in the protocol Section 8.6, and will not be influenced by the results of an interim analysis.

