Table 14.1-1 shows the needed total number of cases at each stage of the two-stage design together with boundaries for early stopping efficacy, calculated on p-value scale using the cumulative error spending function. With ½ information collected at the stage of interim analysis (that is, with exactly 191 confirmed ILIs) the trial would stop early for efficacy if the p-value is lower than 0.00282. Otherwise the trial will be continued and more subjects will be enrolled. The actual boundaries used for decision making would depend on number of confirmed ILIs occurring and reported for Interim Analysis.

Table 14.1-1: Example of a Two Stages Group-Sequential Design

	Stage 1 First Interim	Stage 2 Final
Number of Events	191	382
Alpha Boundary on p-value scale (equivalent to Type 1 error, 1-sided), early stopping for efficacy	0.00282	0.02518

The stopping rules are statistically determined and should be complemented by clinical and strategic stopping rules that allow the DMC to make a decision on a broader picture of the data which includes safety endpoints and the other endpoints of the study being for example secondary efficacy objective 4. Another interim look at the data with appropriate adjustment of type 1 error might be recommended before reaching the targeted 381 cases.

For the interim analyses, if needed a restricted unblinding will be done, i.e. only independent DMC members and unblinded individuals responsible for the analyses will receive access to the randomization codes and unblinded data for the purpose of preparing the interim analyses (further information on handling of the blinding for the interim analyses can be found in the DMC charter [and protocol section 3.3](#)). The results of the interim analyses will be used only for DMC purposes and will not be reported in a CSR.

The comparison of the test statistic with its boundary values will be performed by using the SAS[®] SEQTEST procedure. The boundary information tables calculated by PROC SEQDESIGN at an analysis stage are structured for input to the SEQTEST procedure. At each subsequent stage, the boundary values are derived by using the test information tables created by the SEQTEST procedure at the previous stage. These test information tables are also structured for input to the SEQTEST procedure. PROC SEQTEST can also be used to compute parameter estimates, confidence limits, and p-values after the trial stops.

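### The SAP names two different alpha-spending functions and tables an interim boundary that matches neither, so the early-stopping threshold varies fourfold

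*SAP*

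**What the plan says.** The overall error is one-sided 2.5%, to be protected by error spending (SAP 14.1: "1-sided), for the hypotheses testing for the primary objectives, an error-spending-function will be used"). The SAP then gives three accounts of how it is spent.

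- **SAP 8.3.** "The cumulative error-spending-function to be used is defined as" t^ρ for 0 < t < 1, where ρ "is the power parameter (for this trial chosen as" 2). A worked example for three equally spaced looks follows.
- **SAP 14.1, formula.** The Lan-DeMets O'Brien-Fleming-type function is to be used ("option ERRFUNCOBF in SAS"). Its parameter a equals alpha "for α spending function and β for beta spending function, and where t is the information fraction".
- **SAP 14.1, text and Table 14.1-1.** At half information ("that is, with exactly 191 confirmed ILIs"), "the trial would stop early for efficacy if the p-value is lower than 0.00282". The table row is labelled "Alpha Boundary on p-value scale (equivalent to Type 1 error, 1-sided), early stopping for efficacy" and lists 0.00282 at 191 events and 0.02518 at 382. The boundaries are attributed to the cumulative error-spending function, without saying which one.

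SAP section 5 and protocol section 8.5 refer to O'Brien-Fleming bounds. Protocol section 8.6 requires an error-spending function but does not name one.

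**The concern.** Sections 8.3 and 14.1 are both unconditional, and neither refers to the other. At a first look the p-value boundary equals the alpha spent so far, so two spending functions mean two stopping thresholds. A tabled value that follows from neither adds a third.

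The boundary decides whether a trial done to meet a regulatory requirement stops early and claims efficacy. An interim one-sided p-value of 0.002 or 0.004 would stop the trial under one part of the SAP and continue it under another. Because the SAP does not settle which rule applies, the choice could be made once the interim p-value is known. The level available for the final test depends on the same choice.

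**Working it through.** **Inputs.** One-sided alpha 0.025 (SAP 14.1). Interim at 191 events, t = 0.5 as the SAP states; 191/381 = 0.5013 against the 381-event target. Co-primary margin 30% (null hazard ratio 0.7) and assumed efficacy 50% (hazard ratio 0.5), from SAP sections 5 and 11.1. Allocation 1:1 (SAP 4.1).

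**Interim boundaries.**

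- Section 8.3: 0.025 × t² = 0.025 × 0.25 = **0.00625** (0.00628 at 191/381).
- Section 14.1 formula: 2 × (1 − Φ(z(1 − 0.025/2)/√t)) = 2 × (1 − Φ(2.2414/0.7071)) = 2 × (1 − Φ(3.170)) = **0.00153** (0.00155 at 191/381).
- Table 14.1-1: **0.00282**.

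Ratios: 0.00625/0.00153 = 4.1; 0.00625/0.00282 = 2.2; 0.00282/0.00153 = 1.8.

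**Can the tabled pair 0.00282 / 0.02518 be reproduced?** Final boundaries are solved from the bivariate normal with correlation √t so that total one-sided error is 0.025, unless futility is stated.

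| Construction | Interim | Final |
|---|---|---|
| Section 8.3, ρ = 2 | 0.00625 | 0.0218 |
| Section 14.1 formula, a = 0.025 | 0.00153 | 0.0245 |
| O'Brien-Fleming type, two-sided 0.05 halved, t = 1/2 | 0.00279 | 0.0239 |
| Same, t = 191/381 | 0.00282 | 0.0239 |
| Classical two-look O'Brien-Fleming | 0.00258 | 0.0240 |
| Fixed-shape O'Brien-Fleming, binding futility, 90% power | 0.00282 | 0.02518 |

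Of the constructions tried, only the last gives both tabled values. That this is where the table came from is an inference from the match. The SAP has no futility stopping rule. Without one, the pair 0.00282 / 0.02518 has a one-sided error of 0.0263, above 0.025.

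**Consequence for the co-primary objective at 191 cases.** Given x QIVc cases out of 191, the estimated hazard ratio is x/(191 − x) and the standard error of its log is √(1/x + 1/(191 − x)). The boundary is crossed when [ln 0.7 − ln(x/(191 − x))]/SE exceeds the critical z. At a true hazard ratio of 0.5, x is binomial(191, 0.5/1.5 = 1/3).

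| Boundary | z | Largest x that crosses | Observed VE needed | P(cross) at true VE 50% |
|---|---|---|---|---|
| 0.00625 | 2.498 | 61 | 1 − 61/130 = 53.1% | 37% |
| 0.00282 | 2.768 | 59 | 1 − 59/132 = 55.3% | 26% |
| 0.00153 | 2.963 | 58 | 1 − 58/133 = 56.4% | 21.5% |

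The event-driven normal approximation (SE = 2/√191) gives 51.2%, 53.1% and 54.4% for the observed VE, and 43%, 33% and 26% for the probability. The levels shift with the method; the ordering and a similar spread remain.

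**Level left for the final test.** Holding the total at 0.025 gives 0.0218 after spending 0.00625, 0.0239 after 0.00282 and 0.0245 after 0.00153.

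**The case against.** The strongest defence is that the documents lean one way. Protocol section 8.5, SAP section 5 and SAP section 14.1 all name O'Brien-Fleming, and 14.1 also names the software option. Section 8.3 then looks like leftover text. That is a good reason to keep the O'Brien-Fleming type, but it does not settle the threshold: within section 14.1 the printed formula gives 0.00153 and the table 0.00282.

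For the table, it can be said that 0.00282 is an O'Brien-Fleming-type value if a is taken as two-sided 0.05 and halved at 191/381, that the table is titled an example, and that actual boundaries follow the observed case count. The halved reading departs from the stated one-sided alpha and half information, and its final boundary is 0.0239 rather than 0.02518. The example fixes exactly 191 cases, and the running text repeats the threshold for that count.

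The interim is optional in the SAP, interim data are restricted to the DMC and the unblinded analysis staff, and details go to a DMC Charter that is not available here. It is true that without an interim nothing changes, and that either function controls the error if applied consistently with its own final level. Deliberate choice after the fact is a possibility, not something shown. But SAP section 1 makes the Charter follow the SAP's definitions, and section 14.1 has stopping discussed between the DMC and Senior Management, so the ambiguity is not removed.

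One qualification stands. Stopping requires both objectives to cross, and section 14.1 adds secondary objective 4 and wider considerations. The probabilities above are therefore chances of crossing the co-primary boundary, an upper limit on a rule-based stop. Adding the primary objective should change them little, since its margin is only 20%.

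**Conclusion.** The concern holds. The SAP prescribes two incompatible spending functions and prints a boundary that neither gives on its stated inputs. The one-sided threshold at 191 cases runs from 0.00153 to 0.00625, about 3 percentage points of observed efficacy and, on the binomial calculation, roughly 37% against 21.5% for the chance of crossing at a true efficacy of 50%. The boundary figures rest only on the SAP's alpha of 0.025 and half information. The efficacy and probability figures also rest on 1:1 allocation, similar follow-up in both arms and a Wald limit.

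This must be fixed before any interim analysis. A related but separate conflict belongs in the same edit: section 14.1 tests the final analysis at the full 0.025, while section 11.1 calls for a reduced level after an interim. Testing at 0.025 after spending at the interim gives an overall one-sided error of 0.0255 (14.1 formula), 0.0261 (table) or 0.0280 (8.3).

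**What to change.** 1. Keep one function. The O'Brien-Fleming type in section 14.1, with a = 0.025 one-sided, agrees with SAP section 5 and protocol section 8.5.
2. In section 8.3, delete the t^ρ formula and the three-look example, and refer to section 14.1.
3. Recompute Table 14.1-1 and the sentence above it from that function, without futility: 0.00153 interim and 0.0245 final at t = 0.5 (0.00155 and 0.0245 at 191/381). This also removes a tabled final boundary above 0.025.
4. In section 14.1, replace the full-0.025 final test with the reduced level that section 11.1 requires once an interim has been done. Remove the mention of β-boundaries, since the SAP has no futility rule.

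The cost is SAP wording and one recomputed table; sample size and event targets need not change. The interim threshold falls from the tabled 0.00282 to 0.00153, nearly half, which lowers the chance of crossing at a true efficacy of 50% from about 26% to 21.5%.

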8.4 Immunogenicity Subsets

For the overall study – a total of 7,692 healthy male and female subjects aged ≥ 2 years to < 18 years of age will be enrolled.

Within this randomization, a subset of 444 subjects per season for the third season will be allocated for immunogenicity testing in a 1:1 ratio from either QIVc or non-influenza comparator, as described in [Section 3](#). For the subsequent seasons, the number of subjects enrolled into the immunogenicity subset is maximized at 222 subjects per season.

8.5 Subgroups

The efficacy analyses will be performed stratified for the following subgroups:

- Subjects ≥ 2 to < 4 years of age, ≥ 2 to < 9 years of age, ≥ 2 to < 18 years of age, ≥ 3 to < 18 years of age, ≥ 4 to < 18 years of age, and ≥ 9 to < 18 years of age
- Subjects "previously vaccinated" and "not previously vaccinated"
- Subjects by race
- Subjects by sex
- Subjects by country or region
- Subjects by season/year treated

If, in any subgroup, the number of confirmed ILI cases is < 10 then the statistical analysis in that subgroup will not be performed.

The immunogenicity analyses will be performed stratified for the following subgroups:

- Subjects ≥ 2 years to < 9 years of age
- Subjects with pre-vaccination HI titer $< 1:10$ and pre-vaccination HI titer $\geq 1:10$
- Subjects "previously vaccinated" and "not previously vaccinated"
- Subjects by race
- Subjects by sex
- Subjects by season/year treated

The safety analyses will be performed stratified for the following subgroups:

- Subjects ≥ 2 to < 6 years of age, ≥ 2 to < 9 years of age, ≥ 2 to < 18 years of age, ≥ 3 to < 18 years of age, ≥ 4 to < 18 years of age, ≥ 6 to < 9 years of age, and ≥ 9 to < 18 years of age
- Subjects "previously vaccinated" and "not previously vaccinated"
- Subjects by race
- Subjects by sex
- Subjects by country or region

For by-season analysis, the efficacy/immunogenicity analyses will be presented by Season 1 in which egg-derived seed virus was used, compared to the vaccine efficacy in Seasons 2 and 3, in which cell-derived seed viruses were used. Safety and immunogenicity analyses will also be performed by time periods.

For details regarding the analyses by center please see [Section 8.3](#) above. Analyses by center will be presented in [Appendix 16.1.9 of the CSR](#).

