
enhance the understanding of immune responses to QIVc vaccination. This study is a regulatory requirement to support the licensure of QIVc for use in children ≥ 4 years of age in the United States (US). Children ≥ 2 years of age are enrolled in this study to further evaluate QIVc in a broader age range and to support submissions in various global regions.
 
The purpose of this study is to demonstrate the efficacy (absolute vaccine efficacy [aVE]), immunogenicity, and safety and tolerability of QIVc compared to non-influenza comparator vaccine in subjects ≥ 2 years to < 18 years of age. If there is more than one season, data from all seasons will be combined.
		

Efficacy Objectives:
 
Efficacy will be evaluated in all subjects in relation to cases occurring > 14 days after last vaccination and until the end of the influenza season.
 
Primary Efficacy Objective(s):
 
To demonstrate absolute vaccine efficacy of QIVc versus a non-influenza comparator determined by first occurrence RT-PCR or culture confirmed influenza, due to any influenza Type A and B strain in subjects ≥ 2 years to < 18 years of age.
 
In case of successful demonstration (see section 8.2) of the primary efficacy objective:
 
Co-Primary Efficacy Objective(s):
 
To demonstrate absolute vaccine efficacy of QIVc versus a non-influenza comparator determined by first occurrence RT-PCR or culture confirmed influenza, due to any influenza Type A and B strain in subjects ≥ 3 years to < 18 years of age.
		

Name of Sponsor: Seqirus UK Ltd	Protocol number: V130_12	Generic name of study vaccine(s): Cell-Based Quadrivalent Subunit Influenza Virus Vaccine (QIVc) Meningococcal (Groups A, C, Y, W-135) Conjugate Vaccine (Men ACWY)

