6.1 Study Vaccine(s)

The term ‘study vaccine’ refers to those vaccines provided by the Sponsor or delegate, which will be evaluated as part of the study objectives. The study vaccines specific to this study are described below.

Investigational Vaccine: QIVc

An approximately 0.5 mL dose of QIVc (cell-derived seasonal quadrivalent influenza vaccine) contains nominally 15 µg of hemagglutinin (HA) of each of the 2 influenza type A strains and each of the 2 influenza type B strains for a total of 60 µg of HA in the vaccine. The strain composition will be that recommended by the WHO for quadrivalent influenza vaccines contemporaneous to the timing of the study. The full composition of the vaccine is reported in [Table 6.1-1](#).

Table 6.1-1: QIVc Vaccine Composition

Names of Ingredients	Quantity per dose* (0.5 mL/dose)	Function
Active Ingredients Haemagglutinin (HA) and Neuraminidase (NA) antigens from the influenza virus strains recommended by the WHO / CBER/ CHMP for the respective season Strain A1 Strain A2 Strain B1 Strain B2	≥ 15µg HA (per strain)	Influenza Vaccine
Other Ingredients		
Buffer M (PBS) pH 7.2		
sodium chloride	4.0mg	Isotonic aid
potassium chloride	0.1mg	Isotonic acid
magnesium chloride hexahydrate	0.05mg	Stabilizer
disodium hydrogen phosphate dihydrate	0.646mg	Buffer

Names of Ingredients	Quantity per dose* (0.5 mL/dose)	Function
potassium dihydrogen phosphate	0.1865mg	Buffer
Water for injection	Up to 0.5 mL	diluent

* the quantities indicated in this table reflect the amount in a 0.5 mL dose.

** residues of special relevance: beta-propiolactone, cetyltrimethylammonium bromide and polysorbate 80.

Non-influenza comparator vaccine:

Meningococcal (Group ACWY) Conjugate Vaccine

Menveo® will be used as non-influenza comparator vaccine.

Menveo® is a meningococcal (Groups A, C, Y and W-135) oligosaccharide diphtheria CRM197 conjugate vaccine for intramuscular injection. Menveo is supplied in two vials that must be combined prior to administration, to reconstitute the MenA lyophilized conjugate vaccine component with the MenCYW-135 liquid conjugate vaccine component immediately before administration.

For a comprehensive review of Menveo® please refer to the Summary of Products Characteristics/ Package Insert supplied by Seqirus or delegate; this document should be reviewed by the Investigators prior to initiating the study.

Saline Placebo

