Sample Size for Secondary Immunogenicity Objectives (Immunogenicity Subset):

The immunogenicity study will be performed in the second season and subsequent seasons.

The immunogenicity endpoint is descriptive and the number of subjects aged ≥ 2 to < 9 years of age is maximized at 444 subjects with approximately 400 evaluable subjects, per season for the second season and for the third season. With a 1:1 allocation, approximately 200 evaluable subjects will be enrolled from the active arm and 200 evaluable subjects would be from the non-influenza active comparator arm. Assuming a 10% drop out rate approximately 444 subjects will be enrolled per season. For the subsequent seasons, the number of subjects enrolled into the immunogenicity subset is maximized at 200 evaluable subjects per season (100 from the active arm and 100 from the non-influenza comparator arm). Assuming a 10% drop out rate approximately 222 subjects will be enrolled per every subsequent season after season three (fourth season, fifth season, etc) depending on the duration of the study.

In the case of early study termination, in the event that the number of ILI cases has been reached, the total number of subjects evaluated may be lower than the number of evaluable subjects described per season.

Sample Size for Safety:

With a Safety Population of 2,674 evaluable subjects in the safety set of QIVc, AEs with population rates of 1 in 1,000 have a 93.1% probability of being detected.

Events with population rates of 1 in 893 have a 95% chance of being observed with $n=2,674$. Events with population rates of 1 in 500 have a 99.7% chance of being observed with $n=2,674$.

Sample size calculations were performed using PASS v12.0.2.

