Log-transformed antibodies at Day 1, Day 22, and Day 50 for not previously vaccinated subjects and Day 1 and Day 22 for not previously vaccinated subjects will be modeled using ANCOVA with a factor for vaccination group, baseline-titer, country, and previous influenza vaccination. Adjusted Geometric means and adjusted geometric mean ratios and pertaining two-sided 95% confidence intervals will be calculated based on these models.

Analysis of binary data

Proportions of subjects with HI titers $\geq 1:40$ will be summarized at all time-points.

Percentages of Subjects with Seroconversion: The number and proportion of subjects achieving seroconversion in HI titers from pre-immunization at all-time points at which blood samples were drawn will be summarized.

All secondary endpoints for binary data will be tabulated for each of the influenza vaccine strains and for each of the vaccine groups, including the associated two-sided 95% confidence intervals according to Clopper-Pearson ([Clopper and Pearson 1934](#)).

Secondary immunogenicity objectives will be evaluated based on the FAS (immunogenicity). If the percentage of vaccinated subject excluded from the FAS (immunogenicity) is greater than 5%, a secondary analysis based on the PPS will be performed to complement the FAS.

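### The Season 1 (egg-seed) immunogenicity presentation has no planned sera, and the titre ANCOVA pools seasons without a season term

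*SAP*

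**What the plan says.** **Seed-type presentation.** In SAP 8.5, "the efficacy/immunogenicity analyses will be presented by Season 1 in which egg-derived seed virus was used", and the sentence goes on: "compared to the vaccine efficacy in Seasons 2 and 3, in which cell-derived seed viruses were used".

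**When sera are taken.** SAP 5 says: "The immunogenicity study will be performed in the second season and subsequent seasons". Protocol 8.5 says the same. SAP 5 gives the subset size, which "is maximized at 444 subjects with approximately 400 evaluable subjects, per season for the second season and for the third season", and smaller subsets are planned for later seasons. SAP 3 also names the second and third seasons. SAP 8.4 differs: "a subset of 444 subjects per season for the third season will be allocated for immunogenicity testing".

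**Strains and pooling.** Protocol 6.1: "The strain composition will be that recommended by the WHO for quadrivalent influenza vaccines contemporaneous to the timing of the study". Protocol 7.3 measures HI against the strains homologous to the seasonal vaccine. The background and rationale part of the protocol synopsis says: "If there is more than one season, data from all seasons will be combined".

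**Titre model.** SAP 12.3 models the log titres "using ANCOVA with a factor for vaccination group, baseline-titer, country, and previous influenza vaccination". SAP 8.1 gives the same list plus age group. Neither contains season. For efficacy, SAP 8.1 names season among the stratifying factors modelled as random effects, and SAP 11.1 adjusts for season if the study runs over several.

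**By-season tables.** SAP 8.5 lists season/year treated as an immunogenicity subgroup. SAP 8.1 restricts subgroup tables to unadjusted estimates.

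**The concern.** There are two separate problems.

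First, the SAP promises an immunogenicity presentation for a season in which it plans no blood draws. Left as it stands, that output will be empty, or its omission will have to be explained as a deviation from the SAP.

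Second, the adjusted titre results average over seasons whose antigens may not be the same. If a strain is replaced, a pooled GMT for that vaccine component mixes titres to two antigens and may describe neither. Without a season term, any between-season difference that baseline titre does not explain goes into the residual and widens the intervals. The SAP already treats season as relevant for efficacy but leaves it out of the titre model, and by-season tables carry no adjusted estimate. So no planned result is both adjusted and season-specific.

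**Working it through.** **1. The plan's subset sizes.** With 10% dropout, 400 / 0.9 = 444.4 and 200 / 0.9 = 222.2. These reproduce the stated 444 and 222.

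**2. Planned evaluable sera by season.**

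| Source | Season 1 | Season 2 | Season 3 |
|---|---|---|---|
| SAP 3 and 5, Protocol 8.5 | 0 | about 400 | about 400 |
| SAP 8.4 read alone | 0 | 0 | about 400 |

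Allocation is 1:1, so by SAP 5 the cell-seed side has about 200 + 200 = 400 QIVc sera and the egg-seed side has 0. On either reading the egg-seed side is empty for titres. Efficacy surveillance is not restricted to particular seasons, so the efficacy half is unaffected.

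**3. Season in the models.** Season appears in the efficacy model (SAP 8.1 and 11.1) and in neither of the two ANCOVA lists (SAP 8.1 and 12.3).

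**4. Size of the effect on precision.** The documents give no titre SD and no between-season difference, so these are assumptions: within-season SD of log10 titre 0.5, two seasons of equal size, equal arms, and a season shift d of 0.3 (2-fold) or 0.6 (4-fold) on the log10 scale.

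Shift in both arms: each season sits d/2 from the pooled mean, which adds d²/4 to the variance.
- d = 0.3: sqrt(0.25 + 0.0225) = 0.522, or +4%
- d = 0.6: sqrt(0.25 + 0.09) = 0.583, or +17%

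Shift in QIVc only: d²/4 is added in one arm and 0 in the other, which averages to d²/8.
- d = 0.3: sqrt(0.25 + 0.01125) = 0.511, or +2%
- d = 0.6: sqrt(0.25 + 0.045) = 0.543, or +9%

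The same both-arms formula with an SD of 0.6 and then 0.4 gives +3% to +7% for a 2-fold shift and +12% to +25% for a 4-fold shift. Baseline titre is in the model and would remove part of any of these.

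**5. Meaning of the pooled GMT.** If two equal seasons had GMTs of 80 and 320, the pooled GMT would be sqrt(80 × 320) = 160, a factor of 2 from each. A season main effect alone, averaged over equal seasons, still returns 160. It improves precision but does not give a season-specific GMT. That needs a season-by-vaccine term with estimates reported by season, or a separate fit per season.

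**The case against.** The case against acting is fair in several respects.

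- *The SAP 8.5 sentence is loose drafting.* Its reference side is worded as vaccine efficacy, so the intended comparison may be efficacy only. That stands, and it is why the repair is only a wording change. A reader might infer that the whole egg-versus-cell comparison fails. It does not, because the efficacy half is feasible.
- *Season is already separated.* Unadjusted by-season titres are planned, and seroconversion and the proportion at or above 1:40 are unadjusted throughout, so the by-season binary results lose nothing. This stands. The gap is confined to adjusted GMTs, GMRs and GMT ratios.
- *Results are reported per strain.* SAP 12.3 gives GMTs and GMRs for each strain and vaccine group, which could be read as separating a replaced strain from its successor. SAP 2.2.4 speaks of four strains, which leaves this open. A strain kept across seasons would still be pooled with no season term.
- *A strain change is not documented.* The plan says that composition follows the current recommendation, but lists no strains by season. A change between Seasons 2 and 3 is a reasonable inference, not a stated fact.

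Two stronger readings are also tempting. One is that omitting season biases QIVc against comparator. Allocation in the subset is 1:1, so season does not confound that contrast. The other is that season differences leak into the country effect through uneven participation. The documents give no country-by-season enrolment, so nothing supports it.

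**Conclusion.** Both parts hold, at modest size. The Season 1 immunogenicity presentation cannot be produced from the planned sampling. The adjusted titre estimates are pooled over seasons without season adjustment, and no adjusted by-season estimate is planned.

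No hypothesis, error rate or success criterion is touched: Protocol 8.4.3.3.1 excludes statistical testing and SAP 5 calls the endpoint descriptive. The gain is in the precision and interpretability of secondary results. Under the assumptions stated, omitting season inflates the residual SD by about 2% to 9% with the shift in QIVc only. That is the more natural case, since the comparator arm receives no influenza vaccine. The range is 4% to 17% with the shift in both arms. These are upper figures before the contribution of baseline titre, and they shrink to nothing if titres do not differ between seasons. The SAP 8.4 mismatch on Season 2 is clerical, since that section refers back to SAP 3.

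**What to change.** - **SAP 8.5:** limit the Season 1 versus Seasons 2 and 3 seed-type presentation to efficacy, or state that no Season 1 sera were planned.
- **SAP 8.1 and 12.3:** add season and season-by-vaccine terms to the titre ANCOVA, or fit it separately per season. Report adjusted GMTs, GMRs and GMT ratios by season, and label any pooled GMT as an average over the strains used. Say whether a replaced strain is reported separately from its successor.
- **The same sentences:** settle whether age group is in the model, since SAP 8.1 includes it and SAP 12.3 does not.
- **SAP 8.4:** align with SAP 3 and SAP 5 on Season 2.

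The cost is SAP wording and two model terms. No new data are needed, and by-season tables are already planned. Adjusted by-season estimates would rest on about 200 evaluable subjects per arm in each of Seasons 2 and 3, fewer per estimate than the pooled result. The choice should be fixed before unblinding, so that the handling of season is not decided after titres by arm have been seen.
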